1.1 Synopsis

Title:	HModEx®, a cloud-based, centralized health economic model marketplace to reduce costs and enhance equity in cancer
Grant Number:	1R43CA297808-01
Study Description:	The investigators intend to create and test an interactive prototype of an online health economic model platform, HModEx®™, to house oncology models.
Objectives:	
Primary Objective: Create the HModEx® health economic model platform
 
Secondary Objectives: Conduct usability testing of search, quality and collaboration on the HModEx® prototype for 20 oncology health economic models

Endpoints:	
Primary Endpoint: Iteratively unit test 4 tasks (A) Revise model platform and back end, (B) Refine the model taxonomy/characterization (i.e., ontology) and search module, (C) Revamp submission module, and (D) Implement paid modules) individually to ascertain 100% pass of common functionality (e.g., searching, uploading, and evaluating models) in the system back end and then iteratively perform integration testing via the front-end user interface until 100% pass using the System Usability Scale (SUS), a validated questionnaire.
 
Secondary Endpoints: Measure the success of Aim 2 by (1) completion of 80% of tasks in usability testing with scores of ≥ 68 on the SUS, and (2) satisfaction with the site. Testing will focus on user interaction with the system, emphasizing effectiveness, efficiency, engagingness, error tolerance, and ease of learning. Specifically, the investigators will assess the ability of the project team and Advisory Panel members to log into the platform, configure and manage their modeling projects, and annotate or categorize

20 November, 2025

them in accordance with an ontological index. We will assign panelists to interact with at least 2 randomly selected models and associated data files, iterating on this milestone until the investigators achieve 100% success.

Study Population:

Phase* or Stage: National Institutes of Health (NIH) Small Business Innovation Research Phase I Study

Description of Sites/Facilities Enrolling Participants: 9 Expert Advisory Panel Members (4 from US, 5 from UK/Netherlands)

[figure not shown]
Description of Study Intervention/Experimental Manipulation: Development and test of HModEx® prototype health economic model platform with 9 Expert Advisory Panel members

Study Duration*: 1 year

Participant Duration: 8 months

[figure not shown]
20 November, 2025

1.2 Schema

20 November, 2025

1.3 Schedule of Activities

2 Introduction

2.1 Study Rationale

Annually, healthcare stakeholders spend an estimated \$1B on health economics and outcomes research (HEOR), much of it to create or recreate computerized health economic (HE) models. They use HE models to estimate the incremental costs and benefits of screening methods and treatments, thus identifying the most cost-effective care and facilitating healthcare decision-making in the United States and globally. Value assessment guidelines developed by practitioner organizations (e.g., the American Society of Clinical Oncology), independent technology assessment review groups (e.g., the Institute for Clinical and Economic Review (ICER)), academicians, managed care organizations (MCOs) and other healthcare institutions often incorporate measures of cost (affordability) and/or cost-effectiveness. Decision-makers are increasingly seeking HE models for use across multiple technologies, as demonstrated by the renal cell carcinoma and non-small cell lung cancer pathway pilots led by the National Institute for Health and Care Excellence (NICE) in the UK. We use the term “HE model” to encompass cost-effectiveness analyses (CEAs), budget impact models (BIMs), and the like. Unfortunately, a significant barrier to using HE models has been insufficient access and transparency. Authors often create models for a single purpose, after which they languish in journal archives, health authority databases or various proprietary settings. With appropriate adaptation and validation, these models can be valuable in their application to other decision problems. The dearth of platforms and standards to facilitate the sharing of computer models makes the models inaccessible to peer reviewers, expert readers, public health officials, and decision makers. When the need arises for a new evaluation to inform health policy or value-based pricing (VBP), such as the need to set a drug’s maximum fair price, stakeholders must reinvent HE models instead of updating or reusing existing work. The creation and management of new models produces a siloed process, requiring considerable time (up to a year) and expense. An open source model (OSM) platform and exchange mechanism that catalogs vetted

20 November, 2025

models with adequate documentation and is agnostic of model software eradicates many barriers to access. Several initiatives have attempted to address this issue; however, a unifying mechanism for HE model sharing remains an unmet need, as highlighted by multiple entities, such as ISPOR, Health Technology Assessment International (HTAi), and the Society for Medical Decision Making (SMDM).

2.2 Background

New cancer drugs have long been at the forefront of research and debate about rising healthcare expenditure in the United States; researchers and decision-makers rely on evidence to support fair pricing and ensure patient access. Health economic (HE) models enable decisions about the pricing and reimbursement of new technologies in the US and globally and support efficient and equitable investments. A significant challenge is that decision-makers perceive HE models to lack credibility because of their “black box” nature and lack of validation, preventing evidence from informing practice. Annually, stakeholders spend an estimated \$1B on health economics and outcomes research (HEOR), and there is substantial waste in producing HE models because analysts routinely “reinvent the wheel” for similar decision problems. Sharing models by making their source code openly available would increase credibility and reduce waste for both modelers and Pharma stakeholders. However, prior initiatives have had limited success, partly due to a lack of incentives for model developers to share HE models.

2.3 Risk/Benefit Assessment

2.3.1 Known Potential Risks

There are no known potential risks to the proposed research.

2.3.2 Known Potential Benefits

The benefits are that decision makers will have access to vetted models, which will be more rapid than the typical 9-12 months it takes to develop a model.

2.3.3 Assessment of Potential Risks and Benefits

N/A

20 November, 2025

3 Objectives and Endpoints

The prototype will accomplish 4 tasks: (A) Revise model platform and back end, (B) Refine the model taxonomy/characterization (i.e., ontology) and search module, (C) Revamp submission module, and (D) Implement paid modules.

OBJECTIVES	ENDPOINTS	JUSTIFICATION FOR ENDPOINTS	PUTATIVE MECHANISMS OF ACTION
Primary			
Create an interactive prototype of HModEx®™ using infrastructure from the Tufts CEVR Open-Source Model Clearinghouse framework.	The prototype will accomplish 4 tasks: (A) Revise model platform and back end, (B) Refine the model taxonomy/characterization (i.e., ontology) and search module, (C) Revamp submission module, and (D) Implement paid modules.	To evaluate the endpoints, the investigators will iteratively unit test all 4 tasks individually to ascertain 100% pass of common functionality (e.g., searching, uploading, and evaluating models) in the system back end and then iteratively perform integration testing via the front-end user interface until 100% pass using the System Usability Scale.	N/A
Secondary			
Conduct usability testing of search, quality and collaboration on the HModEx® prototype.	We will use a convenience sample of 20 existing oncology OS models from GitHub, the literature and the Advisory Panel (using a combination of existing ontologies), accessed and analyzed using new settings/populations by 8 of a 10-member Advisory Panel (2 are Pharma only) and evaluated using the AdViSHE validation assessment tool to document model quality.	Measure the success of Aim 2 by (1) completion of 80% of tasks in usability testing with scores of ≥ 68 on the System Usability Scale, a validated questionnaire, and (2) satisfaction with the site. Testing will focus on user interaction with the system, emphasizing effectiveness, efficiency, engagingness, error tolerance, and ease of learning. Specifically,	N/A

20 November, 2025

OBJECTIVES	ENDPOINTS	JUSTIFICATION FOR ENDPOINTS	PUTATIVE MECHANISMS OF ACTION
		the investigators will assess the ability of the project team and Advisory Panel members to log into the platform, configure and manage their modeling projects, and annotate or categorize them in accordance with an ontological index. We will assign panelists to interact with at least 2 randomly selected models and associated data files, iterating on this milestone until the investigators achieve at least 75% success.	
Tertiary/Exploratory			

4 Study Design

4.1 Overall Design

This is a single-arm study that will build and evaluate a health economic model platform prototype using a 10-member expert advisory panel of health economists from the US and Europe. For aim 1, Panelists will be randomly assigned to interact with several models according to key use cases (e.g. model publishing, model searching, user registration, user profile updating, payments, etc.), create wireframes for each of these using Axure RP (or equivalent tool), and create a high level click through prototype of the UI for feedback from Advisory Panel (AP) members. Once the UI has been defined, the investigators will code up each use case and alpha test those with 5 AP members. We plan to build unit tests and end user test scripts to help identify bugs as early as possible in the development process and to aid in debugging. A satisfaction questionnaire, using a Likert-like scale, will be devised to ensure that the Advisory Panel finds that 90% of this key functionality is stable; then, the investigators will begin beta testing with selected end users to gather additional feedback.

For aim 2, a primary test dataset comprising 20 oncology OSMs from the AP members, CISNET and websites will be uploaded into the HModEx® platform, annotated, searched for (using a combination of existing ontologies), accessed, and analyzed. Models that meet the vetting criteria will be triaged to one or more AP members based

20 November, 2025

on their expertise/interests for further validation. The models will be accessed and evaluated for quality using the CADTH validation assessment tool by our 9 modeler AP members. This validation process will include annotation using the ontology module (Aim 1) and activation of a paid module for premium content; for this first phase, the premium content will be simulated and the paid module will be manually administered. The success of Aim 2 will be assessed via the ability to retrieve a model with the requested search characteristics 90% of the time (Aim 2A, 2B) and complete 80% of tasks in usability testing with scores of ≥ 68 on the System Usability Scale, a validated questionnaire⁸³, and satisfaction with the site (Aim 2C). Testing will focus on how users interact with the system, emphasizing effectiveness, efficiency, engagingness, error tolerance, and ease of learning^{83, 84}; remote usability testing will be conducted using screen-sharing technology. Specifically, the investigators will assess the ability for the project team and AP members to log in, configure/manage their modeling projects, annotate or categorize them according to an ontological index and for each AP member to modify/evaluate at least 2 of the 20 oncology models and associated data files (Figure 4). Panel members will be randomly assigned to thus interact with multiple models; the investigators will iterate on this milestone until 100% achieved. A brief report will be produced that will review quantitative results, qualitative findings, and design recommendations for addressing problem areas. This report will be shared with our AP and will inform any necessary product modifications. The Advisory Panel will be charged with the following responsibilities during alpha and beta testing of our proposed platform:

- 6 members alpha testing for 1 hour each@\$200/hr, which includes uploading an oncology model of your choosing
- 5 members beta testing for 2 hours each for 2 models, which includes interacting with 5 models on the platform

The total remuneration for each Advisory Panel member is up to \$2,000 (\$200/hr*2 hrs*5 models) over the course of 6-12 months after formal awarding of the project.

4.2 Scientific Rationale for Study Design

See Study Rationale above.

4.3 Justification for Intervention

N/A

4.4 End-of-Study Definition

Achievement of milestones, as above.

20 November, 2025

5 Study Population

5.1 Inclusion Criteria

10 Expert Advisory Panel members

5.2 Exclusion Criteria

Those not within our already recruited Expert Advisory Panel

5.3 Lifestyle Considerations

None

5.4 Screen Failures

N/A

5.5 Strategies for Recruitment and Retention

The Advisory Panel members have already been recruited from the PI's knowledge base and the ISPOR Open Source Model Special Interest Group.

20 November, 2025

6 Study Intervention(s) or Experimental Manipulation(s)

6.1 Study Intervention(s) or Experimental Manipulation(s) Administration

6.1.1 Study Intervention or Experimental Manipulation Description

See Overall Design above.

6.1.2 Administration and/or Dosing

See Overall Design above.

6.2 Fidelity

6.2.1 INTERVENTIONIST TRAINING AND TRACKING

The user experience (UX)/user interface (UI)/human factors expert, [name], has 19 years of experience in this field. He will be developing clickable grayscale wireframes – sufficient to begin evaluating the product against key user tasks. [name] will then evaluate this prototype via UX study sessions with 6 AP members. An informal summary of findings and observations will be provided, with learnings incorporated into the following iterative prototype. Second Iteration Prototyping and Testing: Based on learnings from the UX studies of the first iteration prototype, [name] and company will collaborate with the programmer to evolve the (or create a new) prototype of the HModEx® platform. The prototype will have higher levels of content, interactive, and/or visual fidelity than the previous prototype, sufficient to validate design changes and continue to evaluate the product against key user tasks. [name] will then evaluate this prototype via UX study sessions with 9 Advisory Panel members. Each participant will be asked to complete a System Usability Scale (SUS) questionnaire at the end of their session. [name] will provide an informal summary of findings and observations, with all learnings incorporated into a final recommendation for Content, Information Architecture, Screen Layout, Interactive Design, and Visual Design for the initial launch of HModEx®.

6.3 Measures to Minimize Bias: Randomization and Blinding

The models will be assigned so as to make sure that the Advisory Panel member to which they are assigned has not previously interacted with this model and has interest in the model subject matter.

6.4 Study Intervention/Experimental Manipulation Adherence

N/A

20 November, 2025

6.5 Concomitant Therapy

N/A

6.5.1 Rescue Therapy

N/A

7 Study Intervention/Experimental Manipulation Discontinuation and Participant Discontinuation/Withdrawal

7.1 Discontinuation of Study Intervention/Experimental Manipulation

Upon achievement of all endpoints for both study aims.

7.2 Participant Discontinuation/Withdrawal from the Study

N/A

7.3 Lost to Follow-Up

N/A

8 Study Assessments and Procedures

8.1 Endpoint and Other Non-Safety Assessments

See study design.

8.2 Safety Assessments

N/A

8.3 Adverse Events and Serious Adverse Events

8.3.1 Definition of Adverse Events

N/A

20 November, 2025

8.3.2 Definition of Serious Adverse Events

N/A

8.3.3 Classification of an Adverse Event

N/A

8.3.3.1 Severity of Event

N/A

8.3.3.2 Relationship to Study Intervention/Experimental Manipulation

N/A

8.3.3.3 Expectedness

N/A

8.3.4 Time Period and Frequency for Event Assessment and Follow-Up

N/A

8.3.5 Adverse Event Reporting

N/A

8.3.6 Serious Adverse Event Reporting

N/A

8.3.7 Reporting Events to Participants

N/A

8.3.8 Events of Special Interest

N/A

8.3.9 Reporting of Pregnancy

N/A

8.4 Unanticipated Problems

8.4.1 Definition of Unanticipated Problems

8.4.2 Unanticipated Problems Reporting

A Data Safety and Monitoring Plan (DSMP) will be developed that will include a brief description of the study design, potential risks and benefits for participating in the study, procedures for data review and reportable

20 November, 2025

events, roles and responsibilities of study staff and the monitoring entity (PI and PhD student), and data management, quality control and quality assurance.

8.4.3 Reporting Unanticipated Problems to Participants

This will be within the DSMP.

9 Statistical Considerations

9.1 Statistical Hypotheses

- Primary Efficacy Endpoint(s):

To evaluate the primary endpoints, the investigators will iteratively unit test all 4 tasks individually to ascertain 100% pass of common functionality (e.g., searching, uploading, and evaluating models) in the system back end and then iteratively perform integration testing via the front-end user interface until 100% pass using the System Usability Scale (SUS), a validated questionnaire.

- Secondary Efficacy Endpoint(s):

We will measure the success of the secondary endpoint by (1) completion of 80% of tasks in usability testing with scores of ≥ 68 on the SUS, and (2) satisfaction with the site. Testing will focus on user interaction with the system, emphasizing effectiveness, efficiency, engagingness, error tolerance, and ease of learning. Specifically, the investigators will assess the ability of the project team and Advisory Panel members to log into the platform, configure and manage their modeling projects, and annotate or categorize them in accordance with an ontological index. We will assign panelists to interact with at least 2 randomly selected models and associated data files, iterating on this milestone until the investigators achieve at least 75% success.

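### The integration-testing half of the primary endpoint takes its 100% pass from the System Usability Scale, which does not record whether a front-end function works

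*Protocol*

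**What the plan says.** The primary endpoint has two halves. The first is back-end unit testing of the four development tasks. It has a stated object: all common functionality must pass, with searching, uploading and evaluating models as the examples. The second half is front-end integration testing. Section 9.1 says the team will "iteratively perform integration testing via the front-end user interface until 100% pass using the System Usability Scale (SUS), a validated questionnaire". The synopsis (section 1.1) has the same rule: "perform integration testing via the front-end user interface until 100% pass using the System Usability Scale (SUS), a validated questionnaire". So does the justification column of the section 3 table: "perform integration testing via the front-end user interface until 100% pass using the System Usability Scale".

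On how the SUS is collected, section 6.2.1 says of the second-iteration sessions with 9 panel members: "Each participant will be asked to complete a System Usability Scale (SUS) questionnaire at the end of their session".

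A SUS cut-off appears only for the secondary endpoint and Aim 2. Section 9.1 has "completion of 80% of tasks in usability testing with scores of ≥ 68 on the SUS", and section 4.1 has "complete 80% of tasks in usability testing with scores of ≥ 68 on the System Usability Scale". Sections 1.1 and 3 give the same value in the same role.

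Section 4.1 also plans functional testing tools: "We plan to build unit tests and end user test scripts to help identify bugs as early as possible in the development process". It does not tie them to the 100% pass. Sections 9.4.1 and 9.4.2 refer back and add no rule.

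**The concern.** Integration testing asks whether the assembled parts work through the user interface: does a search return, does an upload complete, does a payment step run. The result is pass or fail for each function. The SUS, as this protocol uses it, asks a person how usable the system felt after a session. The result is one score per participant. The protocol uses the second kind of result to decide the first kind of question.

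The criterion can therefore go wrong in either direction. It could be met while a front-end function is broken, or missed while every function works. Testing is to be repeated until it is met, and it is one of the milestones whose achievement ends the study (sections 4.4, 7.1 and 10.1.2). If the instrument does not observe what the milestone is about, reaching the milestone does not show that the front end works.

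**Working it through.** The protocol derives no figure for this criterion, so there is nothing to reproduce. The check compares the passages and adds a short illustration.

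**Step 1: object and instrument in each clause of the primary endpoint (section 9.1).**

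| Clause | What is counted | Measured by |
|---|---|---|
| Back-end unit tests | Common functionality | The unit tests |
| Front-end integration tests | Not restated; plausibly the same functionality | The SUS |

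In the first row the instrument fits the object. In the second it does not, because section 6.2.1 makes the participant the unit of the SUS.

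**Step 2: is there a SUS pass rule for the primary endpoint?** The cut-off of 68 is stated in sections 1.1, 3, 4.1 and 9.1, each time for the secondary endpoint or Aim 2. None is stated for the primary endpoint. Step 3 borrows 68 as an assumption.

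**Step 3: can the two measures disagree?**

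Inputs from the protocol:
- 9 SUS raters (section 6.2.1, the only sessions to which the SUS is tied)
- 3 example functions (section 9.1)
- 5 named use cases (section 4.1), as an alternative list
- cut-off of 68 (secondary endpoint)

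Assumptions: exactly one function fails, or exactly one rater scores below 68. The protocol gives no SUS scores or failure rates.

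Share of functions passing = (functions − failures) / functions. Share of raters passing = (raters − raters below 68) / raters.

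- One function fails, all raters reach 68: functions (3 − 1)/3 = 66.7%; raters 9/9 = 100%. With the 5 use cases as the list, functions (5 − 1)/5 = 80.0%.
- All functions work, one rater is below 68: functions 3/3 = 100%; raters (9 − 1)/9 = 88.9%.

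In the first case the SUS criterion is met and the function criterion is missed. In the second it is the reverse. The percentages depend on the length of the list and the number of raters. The disagreement does not: any single failure on one measure takes it below 100% and leaves the other untouched.

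**The case against.** **The denominator is not wholly missing.** The two clauses are parallel, and the natural reading carries common functionality over from the first to the second. This stands. A reader might infer that the 100% is a percentage of nothing in particular, but the text does not support that. The objection does not rescue the criterion, because the sentence then names an instrument that cannot measure functionality.

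**The choice of SUS summary does not by itself decide the endpoint.** A reader might set every rater at 68 or above against a mean of at least 68, and infer opposite verdicts on the same data. With one rater at 60 and eight at 70, the mean is (8 × 70 + 60)/9 = 68.9, so the mean passes while one rater fails. With the low score at 50, the mean is (8 × 70 + 50)/9 = 67.8, and both rules fail. The contrast depends on the assumed low score. A group mean is also not a reading of a 100% pass, since it yields no percentage. The point does not rest on it.

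**Detail may sit in the analysis plan or a test plan.** This stands for the script list and the operational pass rule. It does not cover the choice of instrument, which the protocol fixes in three places.

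**The 90% figure in section 4.1 is not a contradiction.** A reader might set "Advisory Panel finds that 90% of this key functionality is stable" against the 100%. The 90% is a gate to beta testing with its own satisfaction questionnaire, and the two can coexist.

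**Proportion.** This is a single-arm prototype build with no hypothesis test, alpha or power. In section 3 the endpoint column lists the four tasks, and the SUS wording is in the justification column. This stands and limits the severity.

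**Conclusion.** The point holds as a wrongly attached instrument in half of the primary endpoint. The SUS, as section 6.2.1 describes it, gives a per-participant usability score and cannot show that front-end functions work. The rule could be met with a failing function (66.7% of functions passing, with 1 of 3 assumed to fail) or missed with all functions working (88.9% of raters passing, with 1 of 9 assumed below 68). These figures rest on assumed failures and a cut-off borrowed from the secondary endpoint. They show that the measures can part, not how often they will.

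A reader might infer that the whole primary endpoint cannot be judged. The documents do not support that: the unit-test half has its own object and measure. The point should be fixed, but it is a matter of wording and record keeping in a prototype study and does not undermine the design.

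**What to change.** In sections 1.1, 3 and 9.1, define integration success as 100% of a prespecified list of front-end end user test scripts passing. Build the list on the scripts and use cases already in section 4.1, fix it before integration testing starts, and record pass or fail for each script.

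Report the SUS with its cut-off of 68 under the secondary endpoint. If the sponsor wants a usability condition in the primary endpoint as well, state it as a separate criterion with its own unit (for example, participants) and its own cut-off.

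The cost is a wording change in three sections and pass/fail recording of scripts that section 4.1 now plans as an aid to finding bugs. The SUS sessions in section 6.2.1 do not change.

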9.2 Sample Size Determination

This is a convenience sample of 20 models to be evaluated by 9 of our Expert Advisory Panel members.

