10.1.2 Study Discontinuation and Closure

When all study aims/milestones have been achieved.

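### The Aim 2 model-interaction milestone is iterated to 100% in sections 1.1 and 4.1 but only to 75% in sections 3 and 9.1

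*Protocol*

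**What the plan says.** Four places in the protocol set the level at which iteration on this milestone stops:

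- Section 1.1 (Synopsis, secondary endpoints): "iterating on this milestone until the investigators achieve 100% success".
- Section 3 (objectives and endpoints table, secondary row): at least 75% success, in the same words as 9.1.
- Section 4.1 (Overall Design, Aim 2): "the investigators will iterate on this milestone until 100% achieved".
- Section 9.1 (secondary efficacy endpoint): "iterating on this milestone until the investigators achieve at least 75% success".

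Three sections make ending or closing depend on milestones or endpoints: 4.4 ("Achievement of milestones, as above"), 7.1 ("Upon achievement of all endpoints for both study aims") and 10.1.2 ("When all study aims/milestones have been achieved").

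The number of people who could form the base of the percentage also varies. In section 3 the models are "accessed and analyzed using new settings/populations by 8 of a 10-member Advisory Panel". Section 9.2 says "This is a convenience sample of 20 models to be evaluated by 9 of our Expert Advisory Panel members". Section 1.1 describes a panel of 9. Section 4.1 refers to a 10-member panel, 9 modeler members and 5 beta testers, and section 5.1 to 10 members.

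**The concern.** The threshold is the stopping rule for an iterative test, so it determines how many rounds are run. With two values in force, a round that succeeds in at least 75% but fewer than 100% of cases is finished under sections 3 and 9.1 and unfinished under 1.1 and 4.1. Staff following different sections would act differently on the same result, and the team could settle the question after seeing the data.

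Closure is affected too, within limits. Sections 4.4, 7.1 and 10.1.2 require all milestones or endpoints to be met. The conflict therefore decides closure only once every other criterion has been satisfied, and reaching 75% on this milestone alone never closes the study.

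The missing base adds to the problem. Neither percentage can be applied until the protocol says whether success is counted per panelist, per panelist-model pair or per task, and how many of these there are.

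**Working it through.** The protocol gives no sample-size, power or alpha calculation, so there is no planned figure to reproduce. The check compares the text and then counts the results on which the two rules disagree.

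**1. Is it the same milestone?** In 1.1, 3 and 9.1 the sentence opens identically (panelists assigned to at least two randomly selected models and their data files) and differs only in the closing threshold. In 4.1 the 100% statement follows, within the Aim 2 text, the requirement that each panel member work on at least 2 of the 20 models and the random assignment of members to models.

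**2. Does another criterion explain the two figures?** No.
- The 100% pass for unit and integration testing belongs to the primary endpoint.
- The 80% of tasks with SUS of at least 68, and satisfaction, are the numbered Aim 2 success measures.
- The 90% retrieval rate in 4.1 is a separate search criterion.

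**3. Which results give opposite decisions?** For a base of n, the smallest count meeting 75% is ceil(0.75 × n). The 100% rule needs n. The rules disagree from ceil(0.75 × n) to n − 1. The unit of counting is an assumption.

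| Base | n | 0.75 × n | Disagreement | Success rate | Counts |
|---|---|---|---|---|---|
| Beta testers (4.1) | 5 | 3.75 | 4 | 80% | 1 |
| Evaluators (3) | 8 | 6 | 6–7 | 75.0–87.5% | 2 |
| Evaluators (9.2) | 9 | 6.75 | 7–8 | 77.8–88.9% | 2 |
| Panel (4.1, 5.1) | 10 | 7.5 | 8–9 | 80–90% | 2 |
| Pairs, 5 × 2 | 10 | 7.5 | 8–9 | 80–90% | 2 |
| Pairs, 8 × 2 | 16 | 12 | 12–15 | 75.0–93.8% | 4 |
| Pairs, 9 × 2 | 18 | 13.5 | 14–17 | 77.8–94.4% | 4 |
| Pairs, 10 × 2 | 20 | 15 | 15–19 | 75–95% | 5 |
| Pairs, 5 × 5 | 25 | 18.75 | 19–24 | 76–96% | 6 |

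**4. How far apart are the rules?** The protocol gives no success probability, so this is illustration only. Take 9 independent panelists, each succeeding with probability p. The 100% rule is met in one round with probability p^9. The 75% rule is met with probability P(X ≥ 7) = 36p^7(1−p)^2 + 9p^8(1−p) + p^9.

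| Assumed p | 75% rule met | 100% rule met |
|---|---|---|
| 0.75 | 0.601 | 0.075 |
| 0.80 | 0.738 | 0.134 |
| 0.90 | 0.947 | 0.387 |
| 0.95 | 0.992 | 0.630 |

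For p = 0.90 the terms are 0.172 + 0.387 + 0.387 = 0.947 after rounding, against 0.9^9 = 0.387.

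**The case against.** The best case on the other side concerns weight and scope; the threshold conflict itself is not answered.

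- **Page 1 is not available.** The amendment history points to page 1 for the changes of 20 November 2025, and that page is not in the text at hand. It might say which figure was revised. That limits the statement about precedence to the text available, but a change summary would not reconcile four current sections that disagree.
- **Section 4.1 is worded differently.** It speaks of 100% achieved, which could mean that every member completes the assignment rather than a success rate. This is a possible reading. Without 4.1, section 1.1 still contradicts 3 and 9.1.
- **The panel counts overlap.** Nine modelers within a 10-member panel are a subset, which is no conflict. This is fair. Still unreconciled are 8 against 9 evaluators (3 against 4.1 and 9.2) and 9 against 10 members (1.1 against 4.1 and 5.1).
- **The 5 × 5 case is the weakest base.** The milestone asks for at least two models, and no section makes 25 interactions its denominator. Without it, the upper ends fall from 6 counts and 96% to 5 counts and 95%.
- **Section 7.1 is a looser link.** It names endpoints, and in section 3 the 75% sentence sits in the justification column. Sections 4.4 and 10.1.2, which name milestones, support the closure point more directly.
- **Stakes are modest.** This is a single-arm prototype test without a formal hypothesis test, and a 100% result satisfies all four sections. This limits the severity but leaves the stopping rule contradictory.

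**Conclusion.** The concern holds: the plan is wrong as written. One milestone has two incompatible stopping thresholds in current text, and the protocol does not show which was intended.

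The size depends on the unit counted, which the protocol does not define. Per panelist, one or two possible counts per round give opposite decisions; with the 9 evaluators of 9.2 they are 7 and 8. Over all the bases considered, 1 to 6 counts do. How often such a result would occur cannot be stated, because neither the success rate nor the number of rounds is given.

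This should be fixed but is not critical, because the numbered Aim 2 success measures do not use this threshold.

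**What to change.** Before testing starts, the sponsor should choose one threshold and state it identically in 1.1, 3, 4.1 and 9.1. The same sentence should name the unit counted as a success and one denominator that reconciles the 8, 9, 10 and 5 given in 1.1, 3, 4.1, 5.1 and 9.2. As optional tidying, 1.1, 3 and 9.1 could cross-refer to the 90% retrieval criterion in 4.1; this is not part of the repair.

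The direct cost is a wording amendment. If 100% is chosen, more rounds may be needed within the 1-year study and 8-month participant durations (1.1) and the remuneration cap (4.1). The cap is $2,000 / $200 per hour = 10 paid hours per member. Assuming 2 hours per model, as in the remuneration formula of 4.1, this covers one pass through 5 models (5 × 2 = 10 hours) or two passes through 2 models (2 × 2 × 2 = 8 hours). A member who also does the 1-hour alpha test would need 11 hours in the first case, above the cap, and 9 in the second.
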